"Is there a difference in sensitivities of these modifications to detecting strabismic amblyopia versus anisometropic amblyopia?"

Hypotheses

Null hypothesis 1 (H1₀): The new crowding tests do not offer better sensitivity to inter-ocular differences in acuity in amblyopic children, than the Sonksen logMAR test (SLT).

Alternative hypothesis 1 (H1_a): The new crowding tests do offer better sensitivity to interocular differences in acuity in amblyopic children, than the Sonksen logMAR test (SLT).

Null hypothesis 2 (H2₀): There is no difference in the sensitivities of the new tests to detecting strabismic amblyopia, versus anisometropic amblyopia.

Alternative hypothesis 2 (H2_a): There is a difference in the sensitivities of the new tests to detecting strabismic amblyopia, versus anisometropic amblyopia.

The following steps will be taken in order to complete this project:

- 1. Critically appraise relevant literature about the effects of crowding on visual acuity in normal and amblyopic adults and children for first-order and second-order optotypes.
- 2. Design a study to incorporate three suggested modifications to current visual acuity and crowding tests, in a sample of child control and amblyopic participants.
- 3. Statistically analyse the results, comparing those obtained on control and amblyopic children, as well as with data already gathered from normal healthy children. Data from the new tests will be compared with each other and with those obtained using the standard clinical vision test (the Sonksen logMAR Test: SLT).
- Accept or reject the given null hypotheses and discuss impact on clinical practice in a written thesis, as well as disseminate results at scientific conferences and in scientific peer-reviewed journals.

Study design, methods of data collection and data analysis

Study design

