Following completion of the vision tests, participants will be asked if they wish to be involved again with the study. If they do, then they will be tested again following their next Orthoptic review with the ACPOS clinic, or at a time that suits the family best. If they do not, this is the end of their participation.

Consideration of measurement tools, validity and reliability

The results will be generalizable to the entire UK screening population of 3 to 11-year-olds, due to the use of a control group, ensuring external validity.

Participant bias will be controlled and intra-observer reliability maximised using the rigorous set of forced-choice psychophysical testing procedures described above and a single specialized researcher. The researcher is a qualified clinical Orthoptist with many year's experience working with children in vision screening clinics, ensuring that the results will be obtained as accurately and consistently as possible. Test/re-test reliability is ensured by the use of randomization of the order in which the eyes are examined, and counterbalancing the order of the experiments.

Statistical consideration and Data management and analysis

Anonymised data from the 3 experiments will be stored digitally on the experimental computer, which is password protected and only accessible to members of the research team. Data will be compiled in an Excel spreadsheet, ready for analysis.

The data will be analysed using SPSS or Statistica with Repeated Measures Analysis of Variance models. Visual acuities, crowding and critical spacing estimates will be compared between normal and amblyopic groups. Confirmation of normality and sphericity will be assessed with a Shapiro-Wilk test and Mauchley's Test of Sphericity and where necessary, error rates will be adjusted with a Huynd-Feldt Correction in order to ensure that type 1 errors (incorrect rejection of the null hypothesis) are less likely. The rate of improvement of visual acuity, crowding and critical spacing over the treatment period will also be compared (in those participants who opt to complete more than one assessment session) between the three modified tests, and the SLT.

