Potential participants will have been identified by ACPOS clinicians as having anisometropic or strabismic amblyopia. Control participants of similar age will also be recruited via the ACPOS clinic as false positive referrals from the screening service. Healthy volunteers will also be acceptable as control participants. The pool of amblyopes projected for 18 months is n=278; 60% strabismic, n=167 (based on a 2016-2017 Addenbrookes audit).

As the participants will mostly have undertaken the normal screening programme and be following treatment plans as guided by the Royal College of Ophthalmology, these results should be able to be generalised to all UK 3 to 11-year-olds diagnosed with amblyopia.

Eligibility Criteria – Inclusion criteria:

- **Test participants;** Male and female 3 to 11-year-old children diagnosed by ACPOS clinicians as likely having amblyopia (strabismic or anisometropic). They will be tested following 6 weeks (or more) of refractive adaption.
- Control Participants; Male and female 3 to 11-year-old children who have been falsely referred into the Hospital Eye Service (ACPOS) by the visual screening service, or healthy volunteers who have satisfactory visual functions, as per the national screening guidelines.
- All participants must be able to complete the Sonsken logMAR Test (SLT) either verbally or via use of a matching card.

Eligibility Criteria – Exclusion criteria:

- Uncorrected refractive error.
- The presence of any other vision limiting medical condition, not listed in the inclusion criteria.
- Any prior or existing medical history of epilepsy or seizures.

Sample Size:

Based on data produced from previous studies, the outcome data obtained from this study will come from an underlying continuous and normal distribution.

As the first alternative hypothesis is two-tailed, a t-test is appropriate for the calculation of sample size, to find an estimated effect size, with standard deviations known for the visual acuity measures (Hulley and Cummings, 1988). A comparison of means during statistical analysis (Repeated Measures ANOVA) makes this a suitable strategy for determining sample size.

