The effect size is set at 0.100 logMAR, which is the minimum inter-ocular difference that should exist for the participant to be classified as amblyopic (Elliott and Firth, 2009). The standard deviation of the visual acuity measure is set as ± 0.100 logMAR. In adults, visual acuity repeatability measures of ± 0.1 logMAR have been found (Klein et al, 1983; Arditii & Cagenello, 1993; Siderov & Tiu, 1999). Lalor (2018), who used staircase procedures like those proposed, found for children aged 3 to 16 years, standard deviations of ± 0.06 logMAR. Pilot studies with the Crowding Distance Test have suggested even lower standard deviations of the test measures (Waugh et al., 2018).

Using a standardarised effect size of 1 (effect size/sd of measure; or Cohen's d of 1), a significance level or probability of committing a type 1 error (incorrect rejection of null hypothesis), of 0.05; and the probability of committing a type 2 error (incorrect acceptance of null hypothesis) of 0.2 (power of 0.8), a sample size of n=16 participants in each group

30

(amblyopes and control participants) will be required to achieve statistical significance, if a difference exists.

In brief, the data generated will be analysed using a Repeated Measures Analysis of Variance (with Huyndh-Feldt correction for violation of sphericity of variance). In this procedure means are compared. Also post-hoc Tukey comparisons between groups can be made; or a Dunnett test comparing each group (anisometropic; strabismic) to the control group (normal controls)

The above calculation is sufficient for a comparison of means. The second hypothesis involves three distinct groups with independence of observation. An alternative way to estimate sample size is to conduct a one-way ANOVA using an effect size *Cohen's f*, is set at 0.4 (for "large" effect size) to examine for large effect sizes. Once again, the significance level or probability of committing a type 1 error is set at 0.05, and the probability of committing a type 2 error is set at 0.2, to yield a study power of 80%.

Following this power calculation, a sample size of n=21 participants in each group (anisometropic amblyopes, strabismic amblyopes and control participants) will be required to achieve statistical significance, if a difference exists.

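### No multiplicity procedure or decision rule covers the three or four new-test versus SLT contrasts behind Hypothesis 1

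*Combined protocol and SAP*

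**What the plan says.** The synopsis (Study Design) sets three new tests against one another and against the SLT, in order to find the best test or combination. The tests are crowding-enhanced letters, contrast-modulated letters and crowding distance. The Rationale describes a separate comparison with the SLT for each. Experiment 3 measures crowding distance in two formats, trigram and repeated numbers, and does not say which is the main one.

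Under Hypotheses, all of this becomes one composite alternative: "The new crowding tests do offer better sensitivity to interocular differences in acuity in amblyopic children" than the SLT. No rule says whether one, some or all of the new tests must do better. Hypothesis 2 also speaks of the new tests collectively.

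The analysis is a repeated measures ANOVA. The section on statistical considerations says that, where necessary, "error rates will be adjusted with a Huynd-Feldt Correction in order to ensure that type 1 errors" are less likely. Sample Size adds: "Also post-hoc Tukey comparisons between groups can be made", or a Dunnett test of each amblyopic group against controls. An alpha appears only in Sample Size: "a significance level or probability of committing a type 1 error (incorrect rejection of null hypothesis), of 0.05". The same section treats the first hypothesis as two-sided: "As the first alternative hypothesis is two-tailed, a t-test is appropriate for the calculation of sample size".

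**The concern.** H1 rests on several contrasts, each of a new test with the same standard. The procedures that the plan names do not cover them. Huynh-Feldt alters the degrees of freedom of the within-subject F test when sphericity fails. It leaves the error rate across later pairwise contrasts uncontrolled, although the plan presents it as its safeguard against type 1 error. Tukey and Dunnett are aimed at a different factor, participant group.

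The study aims to pick the best test and to discuss the impact on clinical practice. A single favourable contrast among three or four could therefore be reported as support for H1, and nothing in the plan fixes the error rate of such a claim. The gap recurs for H2, where the strabismic versus anisometropic comparison can be made once for each new test.

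**Working it through.** **The plan's own figure.** Inputs from Sample Size: difference 0.100 logMAR, SD 0.100 logMAR, two-sided alpha 0.05, power 0.80. The normal formula gives n per group = 2 × (1.960 + 0.842)² × (0.100/0.100)² = 15.7, so 16, as stated. This is one comparison of two groups at one alpha. It makes no allowance for several new-test versus SLT contrasts.

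**Number of contrasts.** k = 3 new tests, or k = 4 if trigram and repeated-number crowding distance are analysed separately.

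**Ungated contrasts, no true differences.** Assume that each contrast is tested at two-sided 0.05. If they are independent:

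- any false difference, either direction: 1 − 0.95³ = 14.3%; 1 − 0.95⁴ = 18.5%
- false difference favouring a new test: 1 − 0.975³ = 7.3%; 1 − 0.975⁴ = 9.6%

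All contrasts share the SLT, so they are probably positively correlated. A correlation of 0.5 is the natural reference, but the documents give no value. Simulation with equicorrelated normal statistics gives:

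| Assumed correlation | Any false difference, k=3 / k=4 | False win for a new test, k=3 / k=4 |
|---|---|---|
| 0 | 14.3% / 18.5% | 7.3% / 9.6% |
| 0.5 | 12.5% / 15.6% | 6.3% / 7.8% |
| 0.8 | 9.8% / 11.4% | 4.9% / 5.7% |

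The benchmark for the third column is 2.5%, the favourable tail of one two-sided 0.05 test. The excess is about 2 times (4.9/2.5) to 4 times (9.6/2.5).

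**Contrasts only after a significant overall F.** Simulated repeated measures ANOVA, compound symmetry assumed, n = 42 and n = 21:

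- No test differs: any false difference about 4%; false win about 2%.
- One new test truly differs (by 1.5 SD in the simulation): any false difference among the remaining tests about 9% (k=3) or 12.5% (k=4); false win about 5% or 6%. The overall F is then almost always significant, so the gate protects nothing.

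**Power after adjustment.** The first Holm step uses 0.05/3 = 0.0167 or 0.05/4 = 0.0125. Take a paired t-test in all 42 amblyopic children and the plan's 0.1 logMAR as the difference to detect. Two contrast SDs are assumed:

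- 0.14 = √2 × 0.1: two independent inter-ocular differences, SD 0.1 each
- 0.20 = √4 × 0.1: four independent eye-by-test measures, SD 0.1 each

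| Contrast SD | Alpha 0.05 | 0.0167 | 0.0125 |
|---|---|---|---|
| 0.14 | 99% | 98% | 97% |
| 0.20 | 89% | 77% | 73% |

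**The case against.** The strongest reply is that the plan never says each contrast will be tested separately at 0.05. It names a repeated measures ANOVA and states alpha only for sample size. If contrasts followed a significant overall F, error would be near 4% when no test differs. If H1 required every new test to beat the SLT, the error of that claim would not be inflated at all. This stands as far as it goes: per-contrast 0.05, the absence of a gate and a rule that any single win suffices are all inferences. But the plan states no gate and no all-must-win rule either. A gate also fails where the study expects to be, with at least one new test truly different.

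A reader might infer a chance of 10% to 19% of wrongly declaring some new test better. The documents do not support that. The range counts errors in both directions, including a new test falsely found worse. Since the plan calls H1 two-tailed, the favourable error is about 5% to 10%, and at k=3 with correlation 0.8 it is 4.9%. The top of either range also needs four independent contrasts, although the plan mostly counts three tests and all share the SLT.

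Nor does the plan lack multiplicity control altogether. Tukey and Dunnett are named for group comparisons, if only as options. The gap concerns contrasts between tests.

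**Conclusion.** The point holds in limited form. No procedure and no decision rule covers the new-test versus SLT contrasts behind H1, and Huynh-Feldt does not supply one. Under ungated two-sided 0.05 testing, the chance of at least one false difference is about 10% to 18.5%, and of a false win about 5% to 10% against a nominal 2.5%. At correlation 0.5 these are 12.5% to 15.6% and 6.3% to 7.8%. The figures rest on the assumed correlation, on k = 3 or 4, and on a reading of alpha that the plan leaves open. An overall-F gate would be only a partial remedy: about 4% when no test differs, but about 9% to 12.5% among the remaining tests when one does. No separate size has been worked out for H2. This is a worthwhile and cheap improvement to the analysis plan; it does not invalidate the design.

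**What to change.** Add to the statistical section:

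1. H1 is tested in the amblyopic children by paired contrasts, new test minus SLT, of the inter-ocular difference.
2. All measures are put on a common log scale before subtraction. The Rationale gives crowding distance in minutes of arc and the SLT is in logMAR, so crowding distance should enter as the log ratio between eyes.
3. Holm, or a many-to-one Dunnett procedure suited to paired data with the SLT as reference, is applied across all new measures at familywise two-sided 0.05. The plan says beforehand whether the two crowding-distance formats count as one measure or two.
4. Superiority to the SLT is claimed only for tests that survive the adjustment.
5. Holm is applied in the same way across the new tests for the strabismic versus anisometropic contrast (H2).

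The cost is a short paragraph, a defined scale and some power; no new data are needed. With 42 amblyopic children the power loss at the first step is 1 to 2 percentage points if the contrast SD is 0.14. If it is 0.20, the loss is about 12 points (k=3) or 16 points (k=4). Under Holm, later steps use a larger alpha once the first contrast is rejected.

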Finally, crowding distance, the spatial distance over which crowding occurs, in normal foveal (central) vision is small (2-4 arcmin) and cannot be measured with current standard clinical optotypes due to their large size (5 arcmin for 0.0 logMAR acuity) (Danilova and Bondarko, 2007; Huurneman et al., 2012; Siderov, Waugh and Bedell, 2013; Pelli et al., 2016). To get around this difficulty, a new vision test was recently created to quantify the crowding distance or "critical spacing" of crowding (Pelli, Waugh, Martelli et al., 2016). It uses a new "Pelli" font (see Figure 3), which is much thinner horizontally than standard clinical fonts, allowing the optotypes to get closer to each other in physical space. This 'Crowding Distance Test' permits quantification of the critical spacing of crowding for the first time in a clinical population. The new "Pelli" font, each optotype appearing like tall skinny numbers, has already been trialled on 'visually normal' school-aged children (Waugh et al., 2018), but not yet examined on children with greater sensitivity to visual crowding, i.e., amblyopes. The third vision test in the proposed research, will investigate whether or not "crowding distance" measures made in each eye, results in greater inter-ocular differences, leading to better detection of anisometropic and strabismic amblyopia than does the current clinical standard visual acuity test, the Sonksen logMAR test (SLT).

8

Figure 3: 'Pelli' font

By using closer first-order target optotypes, second-order target optotypes, and quantifying crowding distance in paediatric populations, the ability to detect amblyopia and monitor amblyopia treatment, could be significantly improved for the first time since the 1960s. At that time crowding was first quantified in a clinical population of adult amblyopes (Flom, Weymouth and Kahneman, 1963) and was subsequently incorporated into commercially available tests as best practice.

THEORETICAL FRAMEWORK

Clinical Appointment with clinical vision test (SLT) Identification and recruitment of amblyopic and control particpants

Vision tested with modified vision tests

Analysis of results

Research questions and aims

Research question:

"Do the new vision test modifications offer better sensitivity to detection of inter-ocular difference leading to improved detection and monitoring of amblyopia, than the Sonksen logMAR test (SLT)?

Secondary research question:

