The testing session is expected to take 45 to 60 minutes, depending upon the attention span and cooperation of the child; this includes regular breaks and relaxation points. It will not be possible to blind the researcher as to which group test participants have been allocated, as those patients with strabismic amblyopia will likely be easily identified due to the presence of their strabismus.

Background information will be recorded on data collection sheets (Appendix 1), and results of the vision tests are recorded as data files on the experimental/display computer. Participants need only complete one testing session, but may complete to 3 sessions over the 24 month period. Additional sessions would allow for analysis change over time. Participants

are free to decide on the length of their participation and can leave the study at any time.

Background information

Prior to testing, the following relevant clinical information will be taken from the patient's digital medical records, or measured and recorded by the PI who is a registered Orthoptist;

- 1. Age
- 2. Gender
- 3. Diagnosis and Amblyopia subtype
- 4. Identification of fellow and amblyopic eye
- Most recent SLT visual acuity result for each eye, for healthy volunteers this will be assessed by the PI.
- 6. Current refractive correction
- Stereoacuity measurement. For healthy volunteers this will be assessed by the PI to ensure inclusion criteria are met.

This information will be used to identify which group the participant will be recruited to (anisometropic, strabismic or control) and also to aid randomisation of initial testing eye within each group. The participant will also be allocated a participant number and all results will be recorded using this participant number to preserve anonymity.

Randomisation

Each group will undergo covariate adaptive randomisation using minimisation to select which eye will be examined first (Hu et al., 2014). Test participants will have either their Amblyopic eye (AE) or Fellow eye (FE) assessed first for all 3 experiments, and control participants will have either their Right eye (RE) or Left eye (LE) assessed first. This will ensure equal distribution of known confounding variables (e.g. amblyopia density, occlusion regime, gender) for testing order bias between eyes. This minimisation process will allow for better statistical analysis and extrapolation of results. The order of experiments will be counterbalanced to prevent testing order bias.

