A Bland-Altmann analysis will also be used to assess levels of agreement between the different test measures, rather than examination of correlation alone. This is because while a high correlation may be an interesting finding, it does not necessarily indicate agreement between the different test measures (Martin Bland and Altman, 1986).

Study Setting

The study will take place in a first floor clinical room with daylight fluorescent lighting, within the University Eye Clinic on [name], Cambridge; and will take place Monday to Friday, 9am to 5pm.

Clinic Address:

University Eye Clinic,

[name],

Cambridge,

[name]

[contact]

Site	Activities
ACPOS clinic - based at the University Eye	Patient Identification point
Clinic	Potential participants approached and
	given study information leaflets by ACPOS
	clinician.
Experimental/clinical room – based at the	Recruitment, consent, recording of
University Eye Clinic	background information, completion of
	visual acuity testing.

The study room is a modified clinical room. It contains appropriate seating for a participant to be tested as well as sufficient and comfortable space for the presence of the researcher and the participant's parent/guardian. Bathrooms are located on the same corridor, and access to the first floor is available via stairs or a lift. Telephones are present within the testing room and additional staff are present in the building at all times the clinic is open, ensuring that help can be obtained at all times should an unexpected emergency arise. University firstaid is available directly using the phone in the testing room. The clinical suitability of these rooms for the purposes of visual acuity assessment has been evaluated by Anglia Ruskin University and an appropriate risk assessment has been completed.

Sample and Recruitment

Study population and sampling technique:

This study will prospectively examine children who fail vision screenings at school and those already being treated. Amblyopic and control participants (aged 3 to 11 years) will be identified via ACPOS (Addenbrooke's Community Paediatric Ophthalmology Service) hosted by the University Eye Clinic. The ACPOS clinic will be a Patient Identification Centre (PIC), and an information poster will be present in the ACPOS waiting room to alert patients that they may be asked if they would like to participate (Appendix 1).

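### The comparison of improvement rates between tests states no time variable, common scale or noise measure, so it cannot show which test monitors amblyopia better

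*Combined protocol and SAP*

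**What the plan says.** Under Research questions and aims, the main question asks whether the new tests are more sensitive to inter-ocular difference, "leading to improved detection and monitoring of amblyopia". The only analysis text that serves the monitoring part is in Statistical consideration and Data management and analysis: "The rate of improvement of visual acuity, crowding and critical spacing over the treatment period will also be compared", limited to data "in those participants who opt to complete more than one assessment session", and made between the three modified tests and the SLT. The same section opens with the only model named: "The data will be analysed using SPSS or Statistica with Repeated Measures Analysis of Variance models".

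Repeat sessions are optional. Study procedure says participants "may complete to 3 sessions over the 24 month period". The text after Experiment 3 says that, if they wish to continue, "they will be tested again following their next Orthoptic review with the ACPOS clinic, or at a time that suits the family best". Children enter at different stages of care: "This study will prospectively examine children who fail vision screenings at school and those already being treated" (Sample and Recruitment).

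On measurement, Computer generation of visual stimuli gives the letter tests a logMAR score. The Rationale describes normal foveal crowding distance as 2-4 arcmin. Under Background information, the SLT value for clinic patients is the latest one available for each eye. It is taken from the record or measured by the principal investigator, and no date is listed among the items collected.

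The plan does not define the rate, its time axis, the start of the treatment period, a scale common to all tests, or a criterion for better monitoring.

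**The concern.** A rate needs elapsed time. Repeated-measures ANOVA has no place for a continuous time that differs between children, and in its standard form it needs the same set of repeated measurements from every child. It could be used if a rate were first computed per child, but the plan states no such step.

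A claim that one test monitors better also needs more than a larger change. The Rationale expects each new test to widen the difference between the eyes. A test that stretches the difference will also tend to stretch its change over treatment, whether or not it separates true improvement from measurement noise any better. Without a responsiveness measure, the analysis could favour a new test over the SLT simply because its scale is wider. The SLT has a further problem: its value may come from a different date than the session with which it is compared.

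At stake is the monitoring half of the research question. The cross-sectional detection analyses are not affected by this point.

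**Working it through.** **1. The plan's own sample sizes.** Sample Size gives effect 0.100 logMAR, SD 0.100, two-sided alpha 0.05 and power 0.80. The normal formula gives n = 2 × (1.960 + 0.842)² / (0.100/0.100)² = 15.7, so 16 per group as stated (exact t-test power 0.781). For three groups with Cohen's f = 0.4, exact power is 0.798 at 21 per group, so 21 is reproduced to rounding. Both figures are for cross-sectional comparisons. None is given for the rate comparison, and no return rate is stated.

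**2. Units.** Take the same proportional gain of 0.2 log units (assumed) on each kind of test. On a letter test the change is −0.20 logMAR. For crowding distance starting at s arcmin, the change is s × (10^−0.2 − 1) = −0.369 × s:
- s = 2: −0.74 arcmin
- s = 3: −1.11 arcmin
- s = 4: −1.48 arcmin

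The 2-4 arcmin range is the document's figure for normal foveal vision. Raw slopes in arcmin and in logMAR cannot be compared. On a log10 scale all three gains equal 0.2.

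**3. Change against noise.** For two sessions with independent errors, signal-to-noise = change / (SD × √2). Sample Size gives SDs of 0.10 (design value) and 0.06 (children, staircase method); the changes below are assumed.
- 0.15 / (0.10 × 1.414) = 1.06
- 0.12 / (0.06 × 1.414) = 1.41

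The smaller raw change is the more detectable one. Likewise, if a test doubles both change and noise, 0.20 / (0.20 × 1.414) = 0.71, the same as 0.10 / (0.10 × 1.414) = 0.71. This applies among the logMAR tests too.

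**4. SLT dates.** Let sessions be d months apart and the two SLT records d_S months apart. If SLT change is divided by d, the apparent SLT rate is the true rate × d_S/d. It is right only when d_S = d, and the error can go either way. If a child returns before another orthoptic review and the SLT is not re-measured, the same record could serve both sessions. Then d_S = 0 and the SLT shows no change by construction.

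**5. Timing and opt-in.** The three new tests are taken by the same child in the same session, so elapsed time and the decision to return are common to them. Opt-in can still move the size of the rate. Suppose true change has mean 0.10 and SD 0.10 logMAR and half the children return. Odds ratios for returning of 1.5, 2 and 3 per 0.1 logMAR of improvement then shift the returners' mean by about +0.02, +0.03 and +0.04 logMAR, or by the same amounts downward if poor responders return.

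**6. Precision.** To compare change between two tests over two sessions, with four independent errors, the SD of the difference is √4 × SD = 2 × SD. Paired t-test, two-sided 0.05, 80% power, for assumed fractions of the 42 amblyopic children returning:

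| Return | n | Detectable, SD 0.10 | Detectable, SD 0.06 |
|---|---|---|---|
| 25% | 10 | 0.20 | 0.12 |
| 50% | 21 | 0.13 | 0.08 |
| 75% | 32 | 0.10 | 0.06 |
| 100% | 42 | 0.09 | 0.05 |

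At SD 0.10, about 32 of 42 children must return before a difference of 0.10 logMAR is detectable. True variation between children in the difference of changes would make this worse; positively correlated errors would improve it.

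**The case against.** The strongest reply is that the plan is underspecified rather than wrong. A reader might infer that it runs an ANOVA with session number as the factor, treating every second session as the same time point. The documents do not say so. The rate sentence names no model and no session factor, and a per-child slope compared across tests would fit the text. Nor does the spread of change over unequal gaps prove an error: at an assumed 0.02 logMAR per month, change is 0.06 over 3 months and 0.24 over 12, and dividing by time returns 0.02 in both cases. This stands, and the point does not rest on that reading.

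A reader might also infer that self-selection and irregular visits confound the comparison between tests. Among the three new tests they do not by themselves, for the reason in step 5. A reader might further infer that the tests are generally in different units. Only crowding distance is in question. Even there, the arcmin figure is background, and Sample Size mentions that test's SD beside logMAR values, which may point to a log scale.

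Finally, monitoring appears in neither hypothesis nor the synopsis aim, and the opt-in basis is stated openly. That limits the importance of the point. It does not supply a time variable or a responsiveness measure, and it does not align the SLT dates.

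**Conclusion.** The concern holds in this form: as written, the comparison cannot support a statement that any new test monitors amblyopia better than the SLT. Two things undermine the between-test contrast. Raw change is not scaled to noise (or, for crowding distance, clearly to the same unit), and the SLT need not share the session date. Irregular timing, opt-in return and the undefined start of treatment affect how large the rate is and to whom it applies.

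The size cannot be fixed from the documents, which give no rate of change, visit interval or return rate. The illustrations show that the ranking of two tests can reverse once noise is considered (1.06 against 1.41), and that with half the amblyopic children returning only differences of about 0.08 to 0.13 logMAR are detectable. They assume independent errors and that the stated SDs describe within-child noise. The plan should be changed on this point, but the main detection analyses do not depend on it.

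**What to change.** Write the following into the analysis plan:

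- Analyse change against actual elapsed time between measurements, using all available sessions. Use a linear mixed model with continuous time and a random child intercept, adding random slopes only if they can be estimated; per-child slopes are an acceptable alternative.
- Date each SLT by its own recorded date, not by the session date.
- Put all thresholds, including crowding distance, on a log10 scale.
- Compare tests on change divided by each test's within-child SD, with its uncertainty, since few children may contribute to that SD.
- Use the fellow eye as a reference for practice and maturation with caution. Occlusion regime is among the listed confounders, so that eye may itself be under occlusion.
- Report how many children return and compare their baseline with that of non-returners.
- Label the analysis exploratory, because the 63 participants were sized only for the cross-sectional hypotheses.

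The cost is protocol wording and modest analysis work. The sponsor must confirm that session and SLT dates are recorded, since neither is in the list of background items. The monitoring claim becomes weaker.
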